12.5.1.3. Adverse Drug Reaction and Suspected Adverse Reaction

An adverse drug reaction means any AE caused by a drug.

Suspected adverse reaction means any AE for which there is a reasonable possibility that the drug caused the AE. For the purposes of safety reporting, "reasonable possibility" means there is evidence to suggest a causal relationship between the drug and the AE. A SAR implies a lesser degree of certainty about causality than an adverse drug reaction (21 CFR 312.32(a)).

12.5.1.4. Unexpected Adverse Reaction

Seikagaku Corporation is responsible for assessing AEs for expectedness. With regards to reporting to the health authority, an AE is considered "unexpected" when its nature (specificity), severity, or rate of occurrence is not consistent with applicable product information as described in the safety information provided in the protocol and investigator's brochure for SI-613. "Unexpected," as used in this definition, also refers to AEs or SARs that are mentioned in the investigator's brochure as occurring with a class of

drugs or as anticipated from the pharmacological properties of the drug but are not specifically mentioned as occurring with the particular drug under investigation (21 CFR 312.32(a)).

12.5.2. Severity of Adverse Events/Serious Adverse Events

The study site will grade the severity of AEs experienced by study participants on a 3-point severity scale (mild, moderate, or severe), as follows:

- Mild: causes no limitation of usual activities; causes slight limitation of usual activities without medication intervention or with only a brief medical intervention
- Moderate: causes some limitation of usual activities and requires medical intervention
- Severe: prevents or severely limits usual activities, or requires systemic intervention

Note: The terms serious and severe are not synonymous. Serious criteria as defined in Section 12.5.1.2 above serve as a guide for defining regulatory reporting obligations. The term severe is often used to describe the intensity (severity) of a specific event (as in mild, moderate, or severe headache); the event itself, however, may be of relatively minor medical significance. This is not the same as serious, which is based on patient/adverse outcome. Therefore, an AE of severe headache might not be considered serious, but a moderate infection for which a subject is hospitalized should be reported as an SAE.

12.5.3. Relationship to Investigational Treatment

An investigator's causality assessment is the determination of whether there exists a reasonable possibility that the investigational product caused or contributed to an AE and must be provided for all AEs (serious and non-serious).

Seikagaku Corporation's determination of attribution will be used for reporting to the appropriate health authorities. The relation of an AE to study participation will be determined using the descriptors and definitions provided in Table 3.

Table 3: Attribution of Adverse Events

Not Related	The AE is clearly/most probably caused by other etiologies such as participant's underlying condition, therapeutic intervention or concomitant therapy, or the delay between administration and the onset of the AE is incompatible with a causal relation, or the AE started before administration (screening phase). Therefore, there is not a reasonable possibility that the AE was caused by the investigational product.
Related	There is a reasonable possibility that the AE was caused by the investigational product. The expression "reasonable possibility" is meant to convey in general that there are facts (evidence) or arguments to suggest a causal relationship (21 CFR 312.32(a)).

The investigator should decide whether, in his or her medical judgment, there is a reasonable possibility that the event may have been caused by the investigational product. Any AE that is suspected to be related to the investigational product will be classified as an adverse drug reaction.

12.5.4. Collecting and Recording Adverse Events

12.5.4.1. Period of Collection

All AEs, regardless of severity and/or the time of occurrence during the study, are to be recorded on the appropriate AE pages (either "serious" or "non-serious") in the eCRF. Recording of AEs will begin immediately upon a subject's signing the informed consent form and continue through the final study visit. Recording of any adverse drug reaction will continue until the event resolves or stabilizes. The investigator should complete all the details requested, including dates of onset, severity, action taken, outcome, and relationship to investigational product. Each event should be recorded separately.

All AEs and SAEs should be treated as medically appropriate. Adverse events should be followed until stabilization or the final study visit; adverse drug reactions should be followed until resolution or stabilization; and SAEs (regardless of suspected relationship to the investigational product) should be followed until the event resolves, stabilizes, or becomes non-serious.

12.5.4.2. Methods of Collection

Adverse events may be collected as follows:

- Observing the participant
- Questioning the participant in an unbiased and non-leading manner
- Receiving an unsolicited complaint from the participant

An abnormal value or result from a clinical or laboratory evaluation can also indicate an AE if it is determined by the investigator to be clinically significant. If this is the case, it must be recorded in the source document and as an AE on the appropriate AE form(s). The evaluation that produced the value or result should be repeated until that value or result returns to normal or is stabilized and the participant's safety is not at risk.

12.5.4.3. Recording Method

12.5.4.3.1. Adverse Events

All AEs occurring during this clinical study will be recorded by the investigator on the appropriate eCRF in precise medical terms, along with the date of onset and the date of resolution. To avoid vague, ambiguous, or colloquial expressions, the AE should be recorded in standard medical terminology rather than the subject's own words. Whenever possible, the investigator should combine signs and symptoms into a single term that constitutes a single diagnosis. Each AE is to be evaluated for duration, severity, seriousness, and relatedness to the investigational product. The severity of the AE and its relationship to the investigational product will be assessed by the investigator.

The investigator will treat participants experiencing AEs appropriately and observe them at suitable intervals until their symptoms resolve or their status stabilizes. If any medication is administered in response to the AE, this medication should be noted on the concomitant medication eCRF as a concomitant medication administered. The action taken and the outcome must also be recorded. The terms of AE resolution (i.e., recovered/resolved, not recovered/not resolved, recovered/resolved with sequelae, recovering/resolving, fatal, unknown) should also be recorded.

12.5.4.3.2. Serious Adverse Events

Serious adverse events will be recorded on the AE and SAE eCRFs, and health authorities will be notified as outlined in Section 12.5.5.2.

12.5.5. Reporting Adverse Events

12.5.5.1. Reporting Serious Adverse Events to the Sponsor

The following process for reporting an SAE ensures compliance with 21 CFR 312 and ICH guidelines. After learning that a participant has experienced an SAE, the investigator or designee is responsible for reporting the SAE, regardless of relationship or expectedness, within 24 hours of becoming aware of the event. The initial SAE report should include as much information as possible, but at a minimum must include the following:

- Reporter
- Subject identification number
- Study product or intervention
- Serious adverse event term
- Relationship to investigational product
- Reason why the event is serious

Supplemental eCRF pages should be current at the time of SAE reporting: medical history, concomitant medications, demographics, investigational product administration, and death, as applicable.

Unavailable details of the event should not delay submission of the known information. As additional details become available, the SAE eCRF should be updated and re-submitted.

In the event that the eCRF is unavailable, a paper SAE Report Form should be completed and submitted via email or efax within 24 hours of becoming aware of the event. Once the eCRF becomes available, the SAE information should be entered as soon as possible.

SAE Reporting Contact Information:

email:		
	efax:	

12.5.5.2. Reporting Serious Adverse Events to Health Authorities

Seikagaku Corporation or its designated representative will provide Investigational New Drug safety reports to the Food and Drug Administration (FDA) and investigators in accordance with the FDA regulations detailed in 21 CFR 312.32.

12.5.5.3. Reporting Serious Adverse Events to Institutional Review Boards

It is the responsibility of the investigators to promptly notify their respective institutional review board (IRB) of Investigational New Drug safety reports or other matters involving risk to subjects as mandated by the IRB.

12.6. Pregnancy

During the study, all female subjects should be instructed to contact the investigator immediately if they suspect they might be pregnant (e.g., missed or late menstrual period). If pregnancy is confirmed, the subject will be withdrawn from the study and followed until the pregnancy comes to term.

The investigator is responsible for reporting all available pregnancy information to SKK or its designee within 24 hours of becoming aware of the event, although pregnancy itself if not considered an AE. Monitoring of the participant should continue until the conclusion of the pregnancy. Follow-up information detailing the outcome of the pregnancy and the health of the newborn should be reported as it becomes available.

Partner pregnancies of a male subject do not need to be reported.

12.7. Potential Device Malfunctions

SI-613 investigational product is categorized as a combination product that contains HA-DF (drug component) in a pre-filled syringe (device component). If any malfunction of the device components occurs, the following procedure is required.

12.7.1. Malfunction

A malfunction is the failure of a device to meet its performance specifications or otherwise perform as intended. Performance specifications include all claims made in the labeling for the device [21 CFR 803.3]. If any malfunction of the investigational product occurs, the investigational product must not be used. It must be placed back in the original kit and kept until the site receives instructions from SKK or its designee. The investigator or designee will report the details of the malfunction to SKK.

12.7.2. Injuries Caused by Device Malfunctions

After learning that a subject, injecting physician, or the other user has experienced any of the following events caused by a device malfunction, the investigator or designee is responsible for reporting the event(s) to SKK within 24 hours of becoming aware of the event.

• Device malfunction associated with a death or serious injury

A serious injury means an injury or illness that:

- o Is life-threatening
- Results in permanent impairment of a body function or permanent damage to a body structure, or
- Necessitates medical or surgical intervention to preclude permanent impairment of a body function or permanent damage to a body structure
- This includes any adverse event resulting from insufficiencies or inadequacies in the labeling and the directions specified in the Investigational Product & Rescue Medication Manual, or any malfunction of the device component and any malfunction that would be likely to cause or contribute to a death or serious injury if the malfunction were to recur. This includes any event that is a result of a user error or intentional misuse of the medical device.

The investigator or designee will report all the injuries caused by a device malfunction on the appropriate AE pages (either "serious" or "non-serious") in the eCRF.

Protocol v3.0 01-September-2017

Seikagaku Corporation or its designated representative will provide a summary of any reportable device malfunctions associated with a death or serious injury as an Investigational New Drug safety report to the FDA and investigators in accordance with the FDA regulations detailed in 21 CFR 312.32. Any malfunctions leading to death or malfunctions resulting in serious injuries that are considered life-threatening will be submitted to the FDA within 7 calendar days of receipt of the information from the investigator or designee. All other malfunctions leading to a serious injury will be submitted to the FDA within 15 calendar days of receipt of the information from the investigator or designee. Malfunctions not leading to a SAE will be included in the annual report.

13. STATISTICS

13.1. Power and Sample Size Determination

Approximately 80 subjects with symptomatic primary OA of the knee will be randomized. Forty subjects per group (80 total subjects) were calculated to provide an 80% probability that a 3 mm (or greater) treatment difference point effect for the primary endpoint will be observed, but not necessarily at a statistically significant level. This assumes that the true treatment difference is 7.5 mm and standard deviation is 23 mm based on the previous Japanese 613/1022 study.

13.2. Randomization

Immediately prior to injection at Week 0, subjects who meet all eligibility criteria will be randomized to a treatment group using a 1:1 ratio of SI-613:placebo.

Subjects will be randomized using a dynamic procedure by a minimization protocol, ¹⁰ balancing treatment assignment on K-L score, baseline WOMAC VAS pain score, sex, and investigational site.

13.3. Analysis Populations

The analysis populations are defined as follows:

- The safety population is defined as all randomized subjects who received the study injection, analyzed according to the treatments subjects received.
- The intention-to-treat (ITT) population is defined as all randomized subjects who received the study injection, analyzed according to the assigned treatment.
- The per-protocol (PP) population is defined as all ITT subjects who had no major protocol deviations that would affect the primary efficacy assessment. The details of major protocol deviations will be defined in the statistical analysis plan.

The efficacy analyses will be performed on the ITT population. Efficacy analyses of the PP population will be supportive of the ITT analysis.

The safety analyses will be performed on the safety population.

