6.3. Subject Withdrawal Criteria

Subjects will be encouraged to adhere to the protocol and complete all required assessments. A subject will be discontinued from the study for any of the following medical or administrative reasons:

- A treatment-emergent AE or considerable worsening of an AE that, in the judgment of the investigator or medical monitor, represents an unacceptable risk to the subject and warrants stopping the subject's participation in the investigational study. The investigator must follow the subject until the AE resolves or satisfactorily stabilizes.
- Pregnancy.
- Death of subject.
- Poor response of a subject to the investigational product such that the investigator determines that the subject needs treatment that excludes them from the protocol.
- A critical deviation from the inclusion or exclusion criteria that leads the investigator or medical monitor to determine that continued injections of SI-613 or placebo are not appropriate for ethical or safety reasons.
- Having joint replacement of the target knee
- Receiving an IA injection into the target knee joint (e.g., HA, corticosteroids, or chondroprotective agents) during the study.
- Participation in another clinical study.
- Development of human immunodeficiency virus infection (as assessed by a positive test for human immunodeficiency virus) or active hepatitis.

- Development or diagnosis of alcohol or other substance abuse.
- If the investigator judges it impossible to continue the study for a subject because
 - o The subject does not comply with protocol requirements
 - o The subject is lost to follow up
 - o There are technical issues at the site
- Investigator discretion at any time.
- Subject's request.
- Sponsor's discontinuation of the study at a site.
- Premature termination of the study by the sponsor.

Any enrolled subjects desiring to discontinue prior to study completion should be encouraged to continue in the study and adhere to the protocol and subsequent regularly scheduled safety and efficacy evaluations. Subjects who are discontinued outside of any scheduled visit will be encouraged to complete the early termination visit at the time of withdrawal. Subjects who are discontinued during a scheduled visit will be encouraged to complete all assessments for both that study visit and the early termination visit at the time of withdrawal. A subject who withdraws following the injection will not be replaced.

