7.2.2. Randomization / Visit 2 (Week 0; Day 1)

Visit 2 must occur in a 7- to 14-day window following the Screening visit.

The following procedures will be performed at Visit 2:

- Confirm no use of rescue acetaminophen in the previous 2 days and before the visit at the visit date.
- Review the medical history information.
- Review and update the use of prior and current concomitant medications and concomitant
 therapies, confirming that the subject has not used any prohibited medications or
 therapies and has not changed the dose and/or regimen of restricted medications or
 therapies since the previous visit.
- Collect vital signs.
- Collect urine and perform a dipstick urine pregnancy test.
- Collect the acetaminophen container from the previous visit and count acetaminophen usage.
- Collect the subject daily diary and assess compliance.
- Record AEs.
- Perform examination of the target knee.
- Administer the WOMAC.
- Administer the SF-36.
- Administer the PASE.
- Conduct the 50-foot walk test and measure pain immediately following using a 100-mm VAS.
- Confirm that the subject meets all of the inclusion criteria and none of the exclusion criteria and is therefore eligible for the study.

- Randomize the subject.
- Perform the first injection.
 - The subject will be instructed to avoid any strenuous activities (such as jogging, tennis, and other active sports or heavy lifting) and prolonged weight-bearing activities (such as standing for more than 1 hour) for 48 hours following the IA injection.
- Record AEs that have occurred during the study visit.
- Distribute new subject daily diary.
- Distribute new acetaminophen tablets.

7.2.3. Follow-up Visits 3 (Week 1; Day 8 ± 2), 4 (Week 2; Day 15 ± 2), 6 (Week 6; Day 43 ± 6), 8 (Week 10; Day 71 ± 6), and 10 (Week 18; Day 127 ± 14)

The following procedures will be performed at Visits 3, 4, 6, 8 and 10:

- Confirm no use of rescue acetaminophen in the previous 2 days and before the visit at the visit date.
- Review and update the use of concomitant medications and therapies, confirming that the subject has not used any prohibited medications or therapies and has not changed the dose and/or regimen of restricted medications or therapies since the previous visit.
- Collect vital signs.
- Record AEs.
- Collect the acetaminophen container from the previous visit and count acetaminophen usage.
- Collect the subject daily diary and assess compliance.
- Perform examination of the target knee.

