8.2. Investigational Product Packaging and Labeling

All investigational products used in this study will be prepared, packaged, and labeled in accordance with the standard operating procedures (SOPs) of SKK or those of its designee, Good Manufacturing Practice guidelines, International Conference on Harmonisation (ICH) guidelines for Good Clinical Practice (GCP), and applicable regulations.

Investigational products will be supplied by SKK, Japan. These products will be labeled according to US requirements and the established randomization plan. Prefilled syringes of 3.0 mL of SI-613 or 3.0 mL of placebo will be packed into blinded treatment kits containing 3 cartons, each containing a single syringe, 1 for each injection in the study for a single subject. The kits for the 2 treatment groups will be identical and will not reveal whether the syringes inside contain SI-613 or placebo. Investigational product kits will be forwarded to participating sites once all regulatory requirements have been met.

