13.5.2. Missing Data

For the efficacy analysis based on repeated-measures models of continuous endpoints, missing data will be implicitly handled via a mixed-effect model, without explicit imputation. Inferences based on this approach are unbiased under the assumption of missing at random, which is a weaker and more generally true assumption than missing completely at random. Sensitivity analysis based on multiple imputation methods which changes imputation methods by missing pattern such as discontinuations due to AEs, lack of efficacy, and other will be performed for the ITT population.

For the efficacy analysis based on percentages of positive responders, subjects who discontinue the study because of target knee AEs or lack of efficacy and subsequently have missing efficacy data will be classified as nonresponders.

No replacement of any missing data will be made for the safety analyses.

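### Does it matter that the set called ITT leaves out randomised subjects who were never injected?

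*Combined protocol and SAP*

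**What the plan says.** Section 13.3 defines three sets. "The intention-to-treat (ITT) population is defined as all randomized subjects who received the study injection, analyzed according to the assigned treatment". The safety set has the same membership but is analysed by treatment received. The per-protocol set is the part of the ITT set without major deviations. The section adds: "The efficacy analyses will be performed on the ITT population". Section 13.5.2 puts the multiple-imputation sensitivity analysis, which varies its method by missingness pattern, on the same set: "such as discontinuations due to AEs, lack of efficacy, and other will be performed for the ITT population". The primary and secondary analyses in Section 13.4.3 name no other population.

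The definition speaks of one injection although three are planned. I read it as at least one; a subject never injected is out on any reading.

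On timing, Section 13.2 says: "Immediately prior to injection at Week 0, subjects who meet all eligibility criteria will be randomized to a treatment group". Section 7.2.2 lists randomisation after eligibility has been confirmed, and the next item is "Perform the first injection". Section 13.4.2 summarises accountability for all enrolled subjects, including who received each injection and why subjects discontinued.

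**The concern.** An intention-to-treat set is expected to hold everyone randomised, because that is what protects the comparison. A treated-only set is usually defended by saying that the decision not to treat was made blind. Here that defence looks doubtful. Sections 5 and 8.4 say the two products may be told apart in the syringe by their viscosity, and the unblinded injecting physician opens the carton after randomisation.

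There is also a conceivable route to non-injection. Section 12.7.1 says: "If any malfunction of the investigational product occurs, the investigational product must not be used". Section 8.2 describes kits of three cartons, "each containing a single syringe, 1 for each injection in the study for a single subject", so a spare is not obviously at hand. The no-replacement rule in Section 6.3 reads: "A subject who withdraws following the injection will not be replaced". It is silent on a subject randomised but never injected. If such exclusions depended on both arm and prognosis, the primary comparison would be biased, and neither the per-protocol nor the sensitivity analysis would show it.

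**Working it through.** **1. The plan's own figure.** Inputs from Section 13.1: 40 per group, true difference 7.5 mm, SD 23 mm, threshold 3 mm.

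- SE = 23 × √(2/40) = 5.143 mm.
- P(observed difference ≥ 3) = Φ((7.5 − 3)/5.143) = Φ(0.875) = 0.809, which reproduces the stated 80%.

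If one or two subjects drop out of one arm without bias, this becomes 0.808 (39 and 40) or 0.806 (38 and 40).

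**2. Who can keep a randomised subject from being injected?**

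- *The injecting physician.* Section 9.6 requires this person to give the injection and not to disclose the allocation. Section 5 keeps them out of the rest of the study's conduct. Section 6.3 gives them no part in discontinuation.
- *Discontinuation decisions.* Section 6.3 assigns these to the investigator or medical monitor, or to a request or decision by the subject or sponsor. Section 9.6 blinds all site personnel except the injecting physician.
- *Device malfunction.* Section 12.7.1 bars use of the faulty product and has the site keep it until instructed. It does not say that the subject then goes uninjected. Section 9.6 has kits assigned from stock held at the site, through a system that also tracks study drug. Whether a replacement would be supplied is not stated.

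**3. What bias would require.** Suppose k subjects are lost from one arm of 40 and differ from those retained by d standard deviations.

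Shift = (k/40) × d × 23 mm

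SE = 23 × √(1/40 + 1/(40 − k)) = 5.176 mm (k = 1) or 5.210 mm (k = 2)

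| k | d | Shift (mm) | Share of 7.5 mm | Two-sided type I error |
|---|---|---|---|---|
| 1 | 0.5 | 0.29 | 3.8% | 0.0504 |
| 1 | 1 | 0.58 | 7.7% | 0.0514 |
| 2 | 0.5 | 0.58 | 7.7% | 0.0514 |
| 2 | 1 | 1.15 | 15.3% | 0.0556 |
| any | 0 | 0 | 0% | 0.0500 |

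Both k and d are assumptions; the documents give no rate of non-injection and no difference by arm. If the model covariates captured half of the prognostic gap (a further assumption), the shift would halve to between 0.14 and 0.58 mm. The largest type I error would then be about 0.0514 with the SE unchanged, or 0.0528 if the SE also fell by √0.5.

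A loss must depend on both arm and prognosis to matter. Even if one product's syringes failed more often, that alone leaves d = 0 and the comparison unbiased.

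**4. What an all-randomised set would change.** The primary analysis (Section 13.4.3.1) is a direct-likelihood repeated-measures model of the scores from Weeks 1 to 12. A subject with no post-baseline score contributes nothing to it, so redefinition alone leaves the estimate as it is. If uninjected SI-613 subjects were followed and responded like placebo (assumption):

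- k = 1: expected difference 7.5 × 39/40 = 7.31 mm; Φ(4.3125/5.143) = 0.799.
- k = 2: expected difference 7.5 × 38/40 = 7.13 mm; Φ(4.125/5.143) = 0.789.

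That is a slight dilution, with no demonstrated bias removed in exchange.

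**The case for a change.** The best case for acting is that the label is wrong whatever the count. A reader who sees ITT will assume all randomised subjects, and such rules are best fixed before unblinding. A corrected definition, an accountability row by arm and a line in the imputation rules would cost a few sentences. The person most likely to notice a faulty syringe is also the one unblinded person at the site. And the responder rules in Sections 13.4.3.2 and 13.5.2 cover only discontinuation for target-knee adverse events or lack of efficacy, so they would not say how an uninjected subject counts.

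Parts of this stand. Modified ITT is the more accurate name, and the documents do not rule out an uninjected subject. But Section 13.3 states membership in the same sentence as the label, so a reader of the plan is not misled. The rest needs the injecting physician to act against Section 9.6, or a malfunction that somehow selects on prognosis, and the documents support neither. The accountability summary in Section 13.4.2 already counts enrolled and injected subjects and gives reasons for discontinuation, so any gap between the two would come to light. The responder and imputation additions would be rules for subjects who may never exist.

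**Conclusion.** The reading of the text is right: the set called ITT is randomised-and-injected, and no efficacy analysis reaches beyond it. No change follows, because a change would bring no gain. Under the plan as written, the decision not to inject does not rest with the unblinded physician, and randomisation immediately before injection leaves almost no room for exclusions. The expected effect on the primary result is small or nil. The range of 0.29 to 1.15 mm, with type I error up to 0.0556, rests on one or two assumed losses from a single arm and an assumed gap of 0.5 to 1 SD for which no mechanism is documented. This judgement assumes that the roles in Sections 5, 6.3 and 9.6 are followed. It would need another look only if the accountability table showed several uninjected subjects, unevenly split between arms.
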